- iii. **Subject Safety.** Only subjects who are eligible based on pre-defined criteria, an interview and a physical examination, and screening laboratory tests will be enrolled. The consent form details issues related to privacy, withdrawal from studies, and use of blood for genetic analyses among other items. The eligibility criteria are structured to exclude patients who have a greater risk of side effects with clonidine. Interventions (clonidine, colesevelam and anorectal tests) pose a low risk to participants. In our previous study, clonidine was well tolerated by women with FI; dry mouth was the only side effect that occurred more frequently with clonidine than placebo. There is no known drug interaction between clonidine and colesevelam. Patients who are positive for depression by the HAD score will be offered referral to Psychiatry. If the patient endorses suicidal thoughts then we will first and foremost offer support. If the patient is on Mayo campus and in department, we will then have a co-worker page 911 and ask for Security. The study coordinator will contact the principal investigator immediately to alert them that of the situation. The study staff will stay with the patient until Security arrives at the location. If the patient is not on Mayo campus, then the study staff will keep the patient on the line and have a co-worker page 911. Study procedures are conducted by trained and experienced personnel. Monitoring for side effects will be performed by study personnel. The PI will also review side effects. Each study is reviewed and analyzed; study discussions and communications are generally by e-mail and stored.
- iv. **Data Integrity.** Only subjects who are eligible based on pre-defined criteria, an interview and a physical examination will be enrolled. Transcription of data is accurate and complete. Calculations will be standardized and accurate. The study technician will monitor data after every study. The PI will also review data after every 10 studies.
- v. **Subject Privacy.** Subjects will be consented in a private room. Adequate time for questions will be provided.
- vi. **Data Confidentiality.** All records are maintained in password protected electronic files. Hard copies are filed in private offices.
- vii. **Product Accountability.** Research Pharmacy will obtain and dispense medication. Unused medication will be collected from subjects at the end of the study and destroyed.

- viii. **Study Documentation.** Documentation will be per established guidelines during the study (hard copy and electronic data capture). These files will be sampled annually.
- ix. **Study Coordination.** Quarterly debriefing will be conducted to ensure expectations are clear and if educational needs exist.

## **D. Human Subjects**

Only subjects who satisfy stringent inclusion and exclusion criteria and provide written informed consent will be included in the protocol. The consent form details issues related to privacy, withdrawal from studies, and use of blood for genetic analyses among other items. Additional details as follows:

1. **Anorectal assessments** are extremely safe; discomfort, if any during rectal distention is mild and tolerable and the risk of rectal perforation in an uninflamed rectum is negligible.
2. **Clonidine** is generally well tolerated at this dose. In a recent study, we observed that the most common side effect with clonidine was dry mouth (about 70% vs. 4.5% in placebo). Other adverse effects included drowsiness (23% vs 14% in placebo), light headedness (27% vs. 9% in placebo) and fatigue (36% vs. 23% in placebo) although they did not reach statistical significance.
3. **Colesevelam** is generally well tolerated at this dose. The most commonly reported side effects from Colesevelam are constipation, diarrhea, dyspepsia, hypoglycemia (mild and well tolerated), headache, abdominal cramps, nausea, and flatulence and back pain. Their frequency ranges from 8%-40% in different studies.

Patients will be appropriately screened and subjects with an increased risk of complications will be excluded from the study. All side effects will be recorded at the follow-up visit. Since the effects of clonidine and colesevelam in pregnant and nursing women are unknown, women who are pregnant or nursing will be excluded from the study. Women of child-bearing potential will be advised to employ contraceptive measures during the study and a pregnancy test will be checked before beginning clonidine or colesevelam.

Patients who cannot tolerate clonidine 0.1 mg bid will be switched to 0.1 mg once daily (qhs) Clonidine will be discontinued if:-

- (i) Subjects have syncope, or lethargy that interferes with safe performance of the volunteer's activities of daily living; or
- (ii) if the systolic blood pressure drops to < 90 mmHg for patients with a systolic BP between 90 and 130 mmHg, or if systolic BP falls to < 100 mmHg for subjects with a pre-treatment systolic BP > 130 mmHg; or
- (iii) if a subject becomes pregnant during the study.

Patients who cannot tolerate three tablets of 625 mg colesevelam twice daily will have dose reduction by 1 tablet daily until they are able to tolerate the medication. Colesevelam will be stopped if a subject becomes pregnant during the study.

**Data Safety and Monitoring Plan.** The DSMP utilized will adhere to the protocol approved by the Mayo Clinic IRB. We propose the following plan: -

**Data quality and management:** The principal investigator will review all data collection forms on a three-monthly basis for completeness and accuracy of the data as well as protocol compliance.

**Adverse events grading:** The common grading scale listed below will be used to grade AEs:

- 0 No adverse event or within normal limits or not clinical significant
- 1 Mild AE, did not require treatment
- 2 Moderate AE, resolved with treatment
- 3 Severe AE, resulted in inability to carry on normal activities and required professional medical attention

- 4 Life threatening or disabling AE
- 5 Fatal AE

Attribution scale: An adverse event includes both, an expected side effect that is of a serious nature, or an unexpected side effect/ event regardless of severity. All events will be graded as to their attribution (unrelated to protocol, or possibly, probably, or definitely related to protocol). Any event that is reported to either the principal investigator or his designated research associates by the subject or medical staff caring for the subject and which meets the criteria will be documented as such.

**Data Monitoring.** The majority of data generated from these protocols will be from analyses performed in our laboratory or the immunochemical core laboratory. Standard quality control procedures are in place for each assay. The frequency of data review for this study differs according to the type of data and can be summarized in the following table:

Data type	Frequency of review
Subject accrual (adherence to protocol regarding demographics, inclusion/exclusion)	Weekly
Adverse event/safety rates (injuries)	Weekly
Annual report	Yearly for IRB

**4. DNA and RNA analyses.** DNA, RNA and plasma samples will be anonymized before being submitted to the genotyping or RNA Seq assays. Specific information is provided in the consent form regarding storage and future use of the biologic sample. These results will not be added to the written record.

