### 1. Phase 1 (Initial screening)

Patients who consent to participate in the study will visit with the investigator during which a physical examination may be performed. During this visit they will be asked to complete questionnaires designed

to determine whether or not they have FI, the type of FI, screen for anxiety or depression and assess quality of life at baseline. **Those who have diarrhea but not FI as assessed by the questionnaires (i.e. Bristol stool type 6 or 7, or >3 bowel movements/day on average) will be excluded from the study.** Eligible patients who give consent will undergo a urine pregnancy test, a 12 lead EKG, anorectal manometry (if not done at Mayo Clinic in the last 6 months), spot stool sample for microbiota analysis, blood draw for genotyping, assessment of the rectal mucosal microbiota with a rectal catheter, and an optional flexible sigmoidoscopy. Patients will be asked to record their dietary intake for 72 hours prior to collecting the stool sample.

Of these tests in phase 1, only the pregnancy test and EKG will determine whether patients proceed to phase 2. The remaining tests will be used to assess specific aims 2-5. Anorectal manometry will help clarify whether these patients have FI because of weakness of the anal sphincter or rectal hypersensitivity. The spot stool sample and rectal mucosal catheter will be used to assess the microbial diversity in FI. Among patients who have a flexible sigmoidoscopy, the mucosal microbiota will be compared on mucosal samples and a rectal catheter. In an attempt at (i) avoiding situations where we recognize subjects are not eligible to participate when they present at the screening visit and (ii) reduce the time taken for screening visits, we propose, when feasible, to ask participants to complete the questionnaires and a 2 week bowel diary before they come for their screening visit. Subjects will return these questionnaires to us by regular or electronic mail. If subjects are not subsequently consented/enrolled into the study, these items will be destroyed. [This bowel diary is identical to that approved for use later in the study.]

Figure 1. Study design

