### 2. Phase 2 (Completion of bowel diaries)

Patients, who have FI, as documented by the questionnaire during phase 1, are not pregnant, and do not have EKG exclusion criteria documented below will enter phase 2. During this phase, patients will fill out daily bowel diaries to ascertain if they have FI symptoms of sufficient severity. The duration of this phase is variable and ranges from 2-4 weeks as clarified below. Only those patients who meet *all* the following criteria at the earliest weekly review of the bowel diaries starting at week 2 i.e., (i) completion of at least 5 out of 7 days of the diary in the preceding week and 10 out of 14 in the preceding 2 weeks, (ii) experience at least 1 episode of FI per week averaged over 2 weeks, (iii) have a Bristol stool form score  $\geq 3$ , and (iii) an average stool frequency of  $\geq 1$ /day will enter the treatment phase. Patients who have not filled out the minimum number of days of bowel symptoms will be asked to fill out bowel diaries for an additional 2 weeks. Those who satisfy criteria at the end

of the two additional weeks will proceed to Phase 3. Otherwise their participation in the trial will be terminated and they will exit the study.

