### **3. Phase 3 (Treatment Phase)**

Patients who satisfy symptom criteria in Phase 2 will be randomized in a 1:1 ratio to receive either a combination of colesevelam (1.875 gm twice daily) and clonidine (0.1 mg oral twice daily) or an identical placebo for 4 weeks. The randomization, to be prepared by [name], will be balanced on age (<50 vs. ≥ 50 y) and BMI (<30 vs. ≥ 30 kg/m^2). Patients will fill *daily* bowel diaries for the entire duration of the treatment phase and mail them in every week. Patients will be contacted periodically (by phone or email) to assess compliance with medications, with filling bowel diaries and for any adverse events. At the end of the treatment phase, patients will be asked to fill questionnaires pertaining to their quality of life and satisfaction with treatment. During the treatment phase, patients will be allowed to use rescue medication in the form of loperamide to circumvent the potential for withdrawal from the study due to overwhelming symptoms. Patients are allowed to take loperamide (2mg/dose) up to 3 unit doses in a 24 hour period, 5 unit doses in a 48 hour period or 10 unit doses in any 7-day period. Patients will need to record their loperamide usage in the bowel diary.

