### **A. Phase 1**

Inclusion Criteria:

- i) Females aged 18-80 years with urge predominant or combined (i.e. urge plus passive) FI, as defined by a validated questionnaire, for ≥ 1 year duration will be eligible to participate.

Exclusion Criteria:

- (i) History of clinically serious cardiovascular or pulmonary disease or EKG showing 2nd degree atrioventricular block or higher.
- (ii) Current or past history of colon or rectal cancer, scleroderma, inflammatory bowel disease, ischemic colitis, small bowel obstruction, congenital anorectal abnormalities, ≥ Grade 2 rectal prolapse, history of rectal resection or pelvic irradiation

- (iii) Neurological disorders – Spinal cord injuries, dementia (Mini-Mental status score <21), multiple sclerosis, Parkinson's disease, peripheral neuropathy
- (iv) Conditions precluding safe use of clonidine, i.e., symptomatic hypotension, or systolic blood pressure of <100 mm Hg on initial visit in Phase 1 of study
- (v) Colon resection greater than limited resection (e.g. sigmoid colectomy for diverticulitis is eligible but right hemicolectomy is not)
- (vi) Patients who are currently on or anytime in the past have been on colesevelam for FI
- (vii) Malabsorptive bariatric procedures (i.e., Biliopancreatic diversion with or without duodenal switch and Jejunoileal bypass), gastric bypass surgery (i.e., Roux en Y gastric bypass) will be excluded. Those patients who have undergone restrictive procedures (e.g. vertical banded gastroplasty, laparoscopic adjustable gastric banding) however will be eligible to participate
- (viii) Currently pregnant or nursing women Prior history of intolerance to clonidine or colesevelam
- (ix) History of sphincteroplasty, sacral nerve stimulator, previous injection of Solesta for treatment of FI
- (x) Medications
  - .
  - Relative – opioid analgesics , other antihypertensive agents (i.e. if there is concern about synergistic effects and hypotension). Patients using drugs with anticholinergic effects at high doses (e.g. nortriptyline greater than 50 mg/day or amitriptyline greater than 25 mg/day) will be excluded at the discretion of the physician. Patients who use lower doses will be eligible to participate provided the dose will be stable during the study

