### Exclusion criteria:

- (i) Positive urine pregnancy screen

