## **C. Phase 3**

### Inclusion criteria:

- (i) Completion of at least 5 out of 7 days of the diary in the preceding week and 10 out of 14 in the preceding 2 weeks
- (ii) At least 1 episode of FI per week averaged over 2 weeks
- (iii) Average Bristol stool score of 3 or higher
- (iv) Average stool frequency of  $\geq 1$ /day

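### The pregnancy test before study drug has no stated timing, and the only scheduled one is nominally 2 to 5 weeks old at first dose

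*Combined protocol and SAP*

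**What the plan says.** Section D (Human Subjects) describes the effects of both drugs in pregnancy as unknown, excludes pregnant and nursing women for that reason, advises contraception, and adds that "a pregnancy test will be checked before beginning clonidine or colesevelam". It names no visit, window or specimen.

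Section C.1 places one urine pregnancy test, in Phase 1. Of the Phase 1 tests, "only the pregnancy test and EKG will determine whether patients proceed to phase 2". Phase 2 is the diary run-in: "The duration of this phase is variable and ranges from 2-4 weeks as clarified below". The step to treatment is worded as "Patients who satisfy symptom criteria in Phase 2 will be randomized in a 1:1 ratio".

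The eligibility lists in section C.2 follow the same stages:

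- **Phase 1 exclusions:** "Currently pregnant or nursing women".
- **Phase 2 exclusions:** "Positive urine pregnancy screen".
- **Phase 3:** diary items only, for example "At least 1 episode of FI per week averaged over 2 weeks". Neither the inclusion nor the exclusion list mentions pregnancy.

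Section D stops each drug if a participant becomes pregnant. No test at or after drug start appears in the visible text.

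**The concern.** Eligibility is checked in stages, so a criterion applied at Phase 1 need not be repeated at Phase 3. That works for fixed history such as prior surgery. Pregnancy status can change between the Phase 1 test and the first dose, and section D itself ties the test to the start of drug.

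If the Phase 1 test is the one section D has in mind, staff who follow the Phase 3 lists could randomise and dose a woman on a result that is weeks old. The other safeguards do not close this interval. Contraception is advised rather than required. The exclusion of pregnant women, the stopping rules, the periodic phone or email contact and the weekly adverse-event review can act only once a pregnancy is known. What is at stake is exposure of an unrecognised early pregnancy to two drugs whose effects in pregnancy the protocol calls unknown.

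**Working it through.** The plan gives no figure of its own for the age of the test at first dose, so there is none to reproduce. It can be built from the phase lengths.

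**Inputs**

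- Time left in Phase 1 after the test: 0 to 1 week (Table 1 allows up to 1 week for Phase 1).
- Phase 2: 2 to 4 weeks (section C.1, Phase 2; Table 1).
- Where feasible, participants complete "a 2 week bowel diary before they come for their screening visit" (section C.1, Phase 1).
- Delay from the end of Phase 2 to first dose: not given; taken as zero.

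**Age of the test at first dose** = time left in Phase 1 + time in Phase 2.

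- Phases as tabulated: minimum 0 + 2 = 2 weeks; maximum 1 + 4 = 5 weeks.
- If the 2-week pre-visit diary counts toward Phase 2, the remaining run-in is 2 − 2 = 0 to 4 − 2 = 2 weeks. The age is then 0 + 0 = 0 to 1 + 2 = 3 weeks.

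The text does not settle whether the pre-visit diary counts. The 5-week end needs both a full week of Phase 1 and the 2-week extension, which section C.1 gives to women who recorded too few diary days.

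**What controls entry to treatment.** Section C.2.C lists 4 inclusions and 4 exclusions. Three exclusions restate inclusions:

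- missing diary days (more than 2 of 7 or 4 of 14 missing is the converse of 5 of 7 and 10 of 14 completed);
- fewer than one bowel movement daily;
- Bristol score below 3.

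That leaves 4 + 4 − 3 = 5 distinct criteria. All 5 come from the diary and none concerns pregnancy.

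**How many women could be exposed.** The Abstract gives 60 women, and the Power Statement gives about 33 per group, or 2 × 33 = 66. With 1:1 allocation, 60 / 2 = 30 to 66 / 2 = 33 women receive active drug. Only those of child-bearing potential are relevant. Their share is not stated, and eligibility runs from 18 to 80 years, so no number at risk can be derived.

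**Two readings of the section D sentence**

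- It means the Phase 1 test. The wording is met, but the result has the age shown above, and a conception during the run-in would go unseen.
- It means a separate test at drug start. A detectable run-in conception would then be found. What is missing is a place for that test in the schedule.

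**The case against.** The strongest reply is that nothing in the plan is broken. The Phase 1 test comes before study drug, and a positive result blocks entry to the run-in. This stands. A reader might infer that section D conflicts with the schedule; it does not, because the sentence sets no window.

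A reader might also infer that an unrecognised pregnancy could be dosed whichever way section D is read. That fails if the sentence means a test at drug start. Such a test would miss only a conception too recent to detect, and so would the remedy proposed here.

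Nor is it right that a positive result has no stated consequence. Section D excludes pregnant women from the study as a whole and stops each drug if pregnancy occurs. What the Phase 3 lists lack is a step that would bring the pregnancy to light.

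It is also fair to say that the range reaches zero on one reading of the diary rules, that its upper end needs the extension, and that only about half of those randomised receive active drug. Figure 1 and the consent pages are not available, and either could state a test time or firmer contraception instructions.

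These points limit the concern without removing it. In the visible text, no step at Phase 3 entry requires a current result.

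**Conclusion.** The point holds as a timing gap in a safety procedure. It is not a contradiction or a breach of the stated commitment. The only scheduled test is nominally 2 to 5 weeks old at first dose, or 0 to 3 weeks if the pre-visit diary counts toward the run-in. Treatment entry depends on the diary alone, so unless section D intends a separate test at drug start, a conception during the run-in could be dosed unrecognised.

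The conclusion assumes no delay between the end of Phase 2 and first dose, and no test time stated only in Figure 1 or the consent pages. A reader might take all 60 to 66 participants as potentially exposed. The documents do not support that, since about half receive placebo and the age range extends well past child-bearing years. Few women are likely to be affected. This is a minor patient-safety improvement with no effect on endpoint or power.

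**What to change.** For women of child-bearing potential, do or repeat the urine test once the diary criteria are met and before randomisation. Research Pharmacy, which already dispenses the medication, should release study drug only on a recorded negative result. Add a positive urine pregnancy test to the Phase 3 exclusions in section C.2.C, and state the timing in section C.1 (Phase 3) and in section D. If a test at drug start was always intended, the same text changes make that explicit.

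The cost is one inexpensive urine test per such woman. Testing every participant would take about 60 to 66 tests, so the real number is smaller. The documents describe no clinic visit at Phase 3 entry, so a home kit with a reported result or a brief visit may be needed.

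The test should come before randomisation. A positive result is then a screen failure, and the analysis is untouched. After randomisation, the same woman would be an untreated member of the intent-to-treat set. The change does not cover conceptions too recent to detect or those that occur on treatment; for these the plan still relies on contraception advice and the stopping rules.

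### The adverse-event severity scale has gaps and overlaps at Grades 1 to 3, so an event that prevents normal activities can be recorded as mild

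*Combined protocol and SAP*

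**What the plan says.** The Data Safety and Monitoring Plan in section D names a single severity scale: "The common grading scale listed below will be used to grade AEs". Grade 0 covers no event or nothing of clinical importance. The others are:

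- Grade 1: "Mild AE, did not require treatment"
- Grade 2: "Moderate AE, resolved with treatment"
- Grade 3: "Severe AE, resulted in inability to carry on normal activities and required professional medical attention"
- Grade 4: "Life threatening or disabling AE"
- Grade 5: fatal

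Earlier in section D, the first of the reasons for stopping clonidine is: "Subjects have syncope, or lethargy that interferes with safe performance of the volunteer's activities of daily living". None of the listed reasons mentions a grade.

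The attribution paragraph that follows the scale defines what counts: "An adverse event includes both, an expected side effect that is of a serious nature, or an unexpected side effect/ event regardless of severity". Section D also says that all side effects are recorded at follow-up. Under section C.1, Phase 3, adverse events are asked about by telephone or email. Section C.4.iii adds that study personnel monitor side effects and the principal investigator reviews them.

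**The concern.** A severity scale should place every event in exactly one grade, and a higher grade should mean a worse event. Here the criteria change from grade to grade: need for treatment at Grade 1, treatment with resolution at Grade 2, loss of function together with professional care at Grade 3. Criteria built this way need not meet end to end.

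The case that matters most is plausible in this trial. A woman reports by telephone that she has been too lethargic for her usual activities, clonidine is stopped, and she recovers without seeing anyone. Her event is serious enough to end treatment with one study drug, yet on the printed criteria it may be filed in the mildest grade. A safety table by grade would then understate what happened, and two members of staff could grade the same event differently.

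**Working it through.** The plan gives no figure to reproduce, so the check sets the grade wording against the possible kinds of event. Take an event that is clinically significant but not fatal, life-threatening or disabling, so that Grades 0, 4 and 5 are out. Cross three features named in Grades 1 to 3: normal activities prevented (yes or no), professional care required (yes or no), and treatment (not required, required and resolved, required and unresolved). That gives 2 x 2 x 3 = 12 combinations. For the moment, stopping study drug is not counted as treatment.

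| Activities prevented | Professional care | Treatment | Printed criteria met |
|---|---|---|---|
| Yes | Yes | Not required | 1 and 3 |
| Yes | Yes | Resolved | 2 and 3 |
| Yes | Yes | Unresolved | 3 |
| Yes | No | Not required | 1 only |
| Yes | No | Resolved | 2 |
| Yes | No | Unresolved | None |
| No | Yes | Not required | 1 |
| No | Yes | Resolved | 2 |
| No | Yes | Unresolved | None |
| No | No | Not required | 1 |
| No | No | Resolved | 2 |
| No | No | Unresolved | None |

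Three combinations have no grade, two have two grades, and seven have one (3 + 2 + 7 = 12). These count kinds of event, not expected events.

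Now place the clonidine-stopping events in the table:

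- Lethargy that prevents normal activities, with no treatment and no professional care, is in the fourth row: Grade 1.
- Brief syncope that resolves by itself, or lethargy that hampers activities without preventing them, is in the tenth row: also Grade 1.
- If stopping clonidine does count as treatment and the event then resolves, these move to the sixth-from-top type of reasoning only if unresolved; when resolved they are in the fifth and eleventh rows respectively: Grade 2. If they have not resolved, they have no grade.

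Under neither reading does such an event reach Grade 3 without professional care. The three ungraded combinations remain whichever way treatment is read.

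**The case against.** The strongest reply is that the scale need not be read so mechanically. Much of that reply stands.

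- **Grade 1 is permitted, not forced.** The word mild carries meaning of its own. Withdrawal might count as treatment. Contact with study staff and the investigator's review might count as professional care. Disabling might point to Grade 4. The documents settle none of these. That rules out saying such events must be graded 1, but it also means one episode of lethargy could be graded 1, 2, 3 or 4.
- **The scale as a whole does not grade by treatment.** A reader might infer that it does. Treatment separates only Grades 1 and 2, and the test at Grade 1 is need for treatment, not whether it was given. Grade 3 uses function and professional care, and Grades 4 and 5 use outcome.
- **The stopping rule is not contradicted.** A reader might infer a conflict between the grades and the reasons for stopping clonidine. Those reasons do not refer to grade and do not say what is mild. They operate whatever grade is recorded.
- **A count of misgraded events, mostly on active treatment, is not supported.** It is tempting to apply the earlier clonidine study's rates in section D to 30 women per arm (60 in the Abstract, randomized 1:1). For drowsiness, light-headedness and fatigue this gives 30 x (0.23 + 0.27 + 0.36) = 25.8 reports on clonidine, but also 30 x (0.14 + 0.09 + 0.23) = 13.8 on placebo. Placebo would supply 13.8 / 39.6 = 35% of them, and section D says the differences were not statistically significant. The share that limits activities is not given, nor is any rate of syncope.
- **Some of these effects may never be graded.** They are listed as known effects of clonidine, and the plan counts an expected effect as an adverse event only if it is serious. All side effects are still to be recorded.

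None of this fills the ungraded combinations or removes the double requirement at Grade 3.

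**Conclusion.** The scale is wrong as written, but the fault is minor. Three conclusions follow from the printed text:

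- An event that prevents normal activities but needs neither treatment nor professional care meets only the Grade 1 criterion. It can be recorded as mild even when it is a reason to stop clonidine.
- A treated but unresolved event without both Grade 3 conditions has no grade.
- An untreated event with both Grade 3 conditions meets Grades 1 and 3. Treated and resolved events with both conditions overlap in the same way at Grades 2 and 3.

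The first conclusion assumes that withdrawal of study drug is not treatment. If it is, the event is Grade 2 once resolved.

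The consequence is limited to safety reporting. The stopping rule is independent of grade, and neither the endpoints nor the data analysis plan in section C.4 uses grade. Participant protection under that rule and the efficacy comparison are unaffected. The number of events affected cannot be estimated from the documents.

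**What to change.** In the grading text of section D:

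- **Grade 3:** let loss of normal activities suffice, without also requiring professional care. Do not make professional care sufficient alone. Simply replacing 'and' with 'or' would turn any trivial event seen in clinic into a severe one.
- **Grade 1:** limit it to events that do not limit normal activities.
- **Grade 2:** drop the requirement that the event resolved. Include events that limit activities without preventing them, treated or not, so that the narrower Grade 1 does not open a new gap.
- **All grades:** state that the highest grade met applies, and whether stopping or reducing study drug counts as treatment.

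On the adverse-event form, record treatment given, outcome and action taken with each study drug as separate fields. In the report, tabulate by arm, whatever the grade, every event that led to discontinuation or dose reduction. This table is needed because brief syncope with no lost activity and no treatment could still be Grade 1 under the revised scale.

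The clonidine discontinuation criteria are left as they are. The cost is a few lines of text, three form fields and one table, with a slightly higher count of Grade 2 and 3 events.
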